#### Hypotheses to be tested:

- 1. We hypothesize that patient- (e.g., health insurance) and provider-level (e.g., patient-provider race discordance) factors are associated with cardiology referral in URM people living with HIV (PLWH) at elevated CVD risk. The primary outcome measure is visit with a cardiologist after meeting criteria for elevated CVD risk.
- 2. We hypothesize that URM PLWH who are seen by a cardiologist will have better CVD outcomes compared to those without referral. Primary outcomes are blood pressure and lipid control, and secondary outcomes are myocardial infarction, stroke, death and cardiovascular death both individually and as a composite, as a function of whether an individual at elevated CVD risk was seen by a cardiologist prior to first event.
  - a. We hypothesize that guideline-directed care including tobacco cessation counseling, cardiac testing, blood pressure and cholesterol medication management, glycemic control and appropriate use of statins mediate the relationship between cardiology referral and CVD outcomes.
- 3. Aim 3 is not driven by a pre-specified hypothesis.

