## 12 Data analysis & statistical considerations

#### 12.1 Analysis Plan for Aim 1

For this aim, the primary outcome variable is referral to a cardiology specialist within 6 months of baseline. This will be measured as a binary variable, with 'yes' defined if there is documented evidence that a referral is made within 6 months of becoming eligible by CVD risk score and kept within 3 months of referral, and 'no' otherwise. We will also determine the time from baseline to cardiology referral and the time until the first visit with the cardiology specialist.

We will consider a number of patient and provider factors evaluated at baseline that are potentially associated with referral to a cardiology specialist. Patient factors will include demographic factors (age, sex, race, ethnicity), level of ASCVD risk, Charlson comorbidity index, SES (e.g.; 5 digit zip code, health insurance ([yes/no]), type of health insurance (Medicare, Medicaid, private, Ryan White, etc.), and history of keeping appointments during 2 years prior to baseline. Provider factors will include primary management strategy (coprimary management defined as having both an HIV doctor and Primary Care Practitioner vs. HIV provider as primary care), and years of practice since training. Cardiologist availability will be a site-determined variable. Based on prior literature, we are specifically considering sex as a biological variable that may be related to specialty referral. 

Baseline characteristics of the cohort will be summarized overall and by referral status. We will include the patient and provider factors described above, as well as vital signs (including weight, body mass index and blood pressure), laboratory measures (particularly total and HDL cholesterol, CD4 cell count, HIV viral load), and relevant medications (ART and cardiovascular medications). We will document the patterns of HIV related CVD comorbidity in the study population, as the funding opportunity announcement specified.

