Univariable and multivariable logistic regression analysis will be used to identify factors that are most strongly associated with cardiology referral. The patient and provider factors listed above are of primary interest and will be included as covariates in the regression models. Subgroups of primary interest will be defined by race/ethnicity (e.g., Non-Hispanic Black, Hispanic Black, Other) and by Insurance Status (None, Medicare, Medicaid, private, Ryan White, etc.). Univariable and multivariable associations will be reported stratified by sub-groups, and reported with interaction tests between the subgroup and other factors. Statistical significance will be determined at the two-sided 0.05 level.

We will also consider a number of sensitivity analyses to evaluate robustness of our study results to various assumptions. For example, to evaluate the impact of drop-outs we will re-run analyses only including patients with routine follow-up within the health care system (e.g., as evidenced by a certain number of visits during the study period). In another sensitivity analysis, we will extend the period for counting a cardiologist referral from 6months to 12 months. If there are subgroups of patients where referral is extremely common (e.g., very high ASCVD risk) or extremely uncommon (e.g., uninsured patients) then we will evaluate the effect of excluding these subgroups in additional sensitivity analyses.

## 12.1.1 Expected power and sample size for Aim 1

Aim 1 expected power and sample size: Preliminary counts collected from sites suggest that we will identify at least 6,000 adult PLWH of Black/African-American and other URM race/ethnicity. We anticipate that 20-25% of these patients will meet the ASCVD risk threshold and be eligible for inclusion in the population for Aim 1, for an anticipated sample size of 1,200-1,500 patients. Preliminary data from our EHR and clinical experience suggests that 20-25% of those at elevated risk will have been referred to a cardiologist. This would provide at least 80% power to detect an association between cardiology referral, and a binary risk factor with 0.33 incidence, when the odds ratio for the association is 1.6 or greater. With 1,500 eligible patients the power to detect an association with an odds ratio of 1.5 would be >85%.

#### 12. 2 Analysis Plan for Aim 2

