Starting with the population selected for Aim 1, we will create a sub-population by matching patients referred to a cardiology specialist (the primary outcome variable for Aim 1) to similar non-referred patients. The goal of this matching is to balance factors that may be confounders of the relationship between referral and cardiovascular outcomes. We will identify factors found to be associated with cardiology referral from Aim 1, as well as factors that are expected to be associated with outcomes such as, age, race, insurance status/type, ASCVD risk score, and comorbidity index. We will not seek to match on factors that may be associated with referral but unlikely to be directly associated with outcomes. For example, we may not want to match on cardiologist availability by site if this is only related to referral and not independently to outcomes. Variables that potentially modify the effect of referral (e.g., sex, race/ethnicity, insurance status) will be included among the matching factors. Patients will be matched within sites and year of baseline encounter.

For each patient referred to a cardiologist we will identify one non-referred patient (1:1 matching) within each site. We will match using values of the individual confounders, with an exact match on sex, race/ethnicity, insurance status/type, and to within a small caliper for continuous variables (e.g., ±5 years for age). Matched pairs will be identified using optimal matching. If this approach fails to identify an adequate number of matched pairs, then 1:1 matching will be implemented using a propensity score.

Once the matching has been implemented, the same baseline characteristics reported for Aim 1 will be summarized in the matched cohort by referral status. Metrics (e.g., standardized differences) will be reported to evaluate how well-balanced the referred and non-referred groups.

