For this aim, the primary outcome variable will be blood pressure control based on prevailing guidelines during the study period (blood pressure <140/90 mmHg). The co-primary outcome is lipid control, defined by prevailing guidelines during the study period. These outcomes will be evaluated longitudinally during 5-years of follow-up. Secondary outcome variables include time to the first major adverse cardiovascular event (MACE = cardiovascular death, myocardial infarction (MI)), stroke, heart failure hospitalization, peripheral artery disease procedure, coronary artery disease (based on diagnosis codes or coronary artery revascularization procedure), and all-cause death. Events ascertained from relevant diagnosis and procedure codes, and from a query of the National Death Index Plus, State Death records, Social Security Death Masterfile, Hospital death record and/or similar death record for causes of death including cardiovascular

death. We will also evaluate time to BP control and time to lipid control among patients who were not controlled at study start. For this Aim, "time zero" for the matched patient pair will be defined as the time from baseline (see Aim 1) when the referred patient kept their cardiology appointment. Events will be ascertained starting from time zero and until the end of follow-up. For each patient, end of follow-up will be defined as the date of the last outcome event or health system encounter without an event, occurring ≥3 months prior to the retrospective study review period of December 31, 2020 of the EHR.

To evaluate the association between cardiology referral and subsequent blood pressure and lipid control (coprimary outcomes), we will first evaluate these measures between referred and non-referred patients at baseline, and then compare prevalence and time trends between referred and non-referred patients using methods appropriate for longitudinal data analysis. For example, we will explore whether the proportion of patients with adequately controlled BP at each year is higher in referred compared to non-referred patients. Because these analyses are conducted in the matched population, the results are adjusted for the potential confounders included in the identification of the matched pairs.

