To evaluate the association between cardiology referral and CVD events (secondary outcomes), the cumulative incidence of primary and secondary outcomes will be summarized in the referred and matched non-referred patients. Follow-up will be censored at the earliest of 8 years or end of follow-up. For each outcome variable a Cox regression model will be fit, and the hazard ratio (referral vs. not referred) and 95% CI, and p-value will be reported. The Cox regression analysis will account for the matched pairs design using the empirical sandwich variance estimate. Statistical significance will be determined at the two-sided 0.05 level.

The relationship between referral status and outcomes will also be evaluated within subgroups of primary interest: sex, race, ethnicity and insurance as defined in Aim 1. Evidence for a differential association between referral status and CVD outcomes for different subgroups will be quantified using an interaction test in the Cox regression analysis. The considerations and approaches outlined in Aim 1 regarding missing data and sensitivity analyses will also be applicable for Aim 2.

#### 12.2.1 Expected power and sample size for Aim 2

Aim 2 expected power and sample size: With an anticipated cardiology referral rate of 20-25% among 1,200-1,500 patients included in Aim 1, the sample size in the matched cohort study is expected to be 250-375 per group. These patients will be accrued into the study over 5 years (2012-2016) and then followed to evaluate BP and lipid control, and for cardiovascular events for up to 8 years through December 31, 2020. For the primary endpoints, the rates in the non-referred group are anticipated to be 30% and 45% for BP and lipid control, respectively. With 300 per group, the study is predicted to have >70% power to detect a 10% increase in rate of BP control, and >95% power to detect a 15% increase in rate of lipid control due to cardiology referral. For the secondary endpoints, the rate of MACE events is anticipated to be fairly low (i.e., a cumulative incidence ~5% at 5 years and ~10% at 10 years) and we anticipate modest power to detect even large reductions in risk of CVD events due to cardiology referral. However, this aim will provide useful information about clinical event rates and estimates of the potential to effect event rates that could be attributed to cardiology referral.

#### 12. 3 Analysis Plan for Aim 3

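### Aim 2 fixes referral status early and has no rule for controls who see a cardiologist later, so it estimates early kept referral, not the exposure worded in hypothesis 2

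*Combined protocol and SAP*

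**What the plan says.** **Exposure.** Section 12.2 forms the Aim 2 cohort by "matching patients referred to a cardiology specialist (the primary outcome variable for Aim 1) to similar non-referred patients". Section 12.1 codes that variable as yes if "a referral is made within 6 months of becoming eligible by CVD risk score and kept within 3 months of referral, and 'no' otherwise".

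**Time zero and follow-up (12.2).** Time zero for a pair "will be defined as the time from baseline (see Aim 1) when the referred patient kept their cardiology appointment". For blood pressure and lipid control, "These outcomes will be evaluated longitudinally during 5-years of follow-up". For events, "Follow-up will be censored at the earliest of 8 years or end of follow-up". The individual cut-off that this refers to is set out separately: "end of follow-up will be defined as the date of the last outcome event or health system encounter without an event". The Cox models compare the two fixed groups. None of these rules mentions a later cardiology visit by a control.

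**Hypothesis.** Section 4, hypothesis 2, concerns patients seen by a cardiologist compared with those without referral, and words the outcomes "as a function of whether an individual at elevated CVD risk was seen by a cardiologist prior to first event". It sets no window.

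**Nearest provision.** Among the Aim 1 sensitivity analyses, "we will extend the period for counting a cardiologist referral from 6months to 12 months". Section 12.2 carries the Aim 1 sensitivity approaches over to Aim 2 in general terms.

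**The concern.** The control group is defined by what did not happen in a short window and is then followed for years. It includes patients referred at month 7, patients who attended more than 3 months after referral, and patients first seen in year 2 or later. All are analysed as non-referred throughout. Under the wording of hypothesis 2, a control first seen in year 2 with no earlier event counts as exposed.

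Two timing gaps follow from the same definition. First, control status depends on up to 9 months of information after baseline (6 + 3), while the pair's time zero may fall earlier in that window. Second, nothing requires the control to be unseen at time zero.

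What is at stake is interpretation. If the groups do not differ, or a difference fades over the yearly comparisons, the planned outputs would not show whether referral had no lasting effect or whether controls had also come under cardiology care.

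**Working it through.** **1. How the plan classifies particular patients**

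| Patient (no event before the visit) | Aim 2 status (12.1, 12.2) | Hypothesis 2 wording (section 4) | Status if the referral window is 12 months |
|---|---|---|---|
| Referred month 4, seen month 6 | Referred | Seen | Referred |
| Referred month 7, seen month 9 | Non-referred | Seen | Referred |
| Referred month 1, seen month 5 | Non-referred (kept after 4 months) | Seen | Non-referred if the 3-month rule stays |
| First referred and seen in year 2 | Non-referred | Seen | Non-referred |

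The third patient could be matched to a referred patient whose time zero is month 8. That control would already have been seen at time zero.

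**2. The plan's own power (12.2.1)**

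Inputs: 300 per group; control rates 30% (blood pressure) and 45% (lipids); increases of 10 and 15 points; two-sided 0.05. I treat the groups as independent.

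Power = Φ[(d − 1.96·SE0)/SE1], where SE0 = √(2·p̄(1−p̄)/n), SE1 = √((p0(1−p0) + p1(1−p1))/n), and p̄ is the mean of p0 and p1.

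- Blood pressure: SE0 = √(2·0.35·0.65/300) = 0.0389; SE1 = √((0.21 + 0.24)/300) = 0.0387; Φ[(0.10 − 0.0763)/0.0387] = 72.9%. The plan states >70%.
- Lipids: SE0 = √(2·0.525·0.475/300) = 0.0408; SE1 = √((0.2475 + 0.24)/300) = 0.0403; Φ[(0.15 − 0.0799)/0.0403] = 95.9%. The plan states >95%.

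Both stated figures reproduce.

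**3. Illustration of dilution**

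The documents give no late-visit rate. I assume a constant rate r of 3%, 5% or 8% of controls per year first seen after time zero, each gaining the full planned effect.

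- Crossed over by year t: c(t) = 1 − exp(−r·t).
- Average over years 0 to 5: c̄ = 1 − (1 − exp(−5r))/(5r).
- Diluted control rate: p0 + c·(p1 − p0).

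Example, r = 5%: c(5) = 1 − exp(−0.25) = 22%, and c̄ = 1 − 0.221/0.25 = 12%. With c̄ the blood pressure control rate is 0.30 + 0.115·0.10 = 0.3115 and the difference is 8.8 points.

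| r per year | c̄, years 0–5 | BP power | Lipid power | c at year 5 | BP power | Lipid power |
|---|---|---|---|---|---|---|
| 3% | 7% | 66% | 93% | 14% | 60% | 89% |
| 5% | 12% | 62% | 90% | 22% | 51% | 82% |
| 8% | 18% | 56% | 86% | 33% | 40% | 70% |

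If a crossed-over control gains half the effect, blood pressure power is 70%, 68% or 65% with averaged crossover, and 66%, 62% or 57% at year 5. The stated bounds have little slack: 5% crossover with full effect gives 68% and 94%.

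**The case against.** **The hypothesis can be read more loosely.** It also speaks of patients without referral, and counting events from the kept visit ensures that every referred patient was seen before any counted event. Section 12.2 can be read as putting the hypothesis into practice with a window, and early versus no early referral is a legitimate contrast. Classifying patients by any visit before an event would bring in immortal time. All of this stands. The gap is that the plan does not name the contrast it estimates, and no planned analysis handles later visits.

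**Direction.** A reader might infer that crossover must pull results toward no effect, so that any fading benefit is contamination. The documents do not support that. Later visits may be prompted by worsening risk, and requiring no kept referral through the whole window removes some early crossover. Nor do the entry criteria describe uncontrolled patients: section 7.3.1 requires a modifiable risk factor, not lack of control.

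**Rate.** Section 5 says these populations are least likely to be referred, and that people with HIV have been reluctant to seek care outside their HIV provider. Late crossover could be small.

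**Size.** A reader might take the year-5 column as the expected loss. It is close to a worst case, because it assumes full benefit and a test at year 5 only, while the plan describes a longitudinal comparison. It also keeps 300 per group, although patients entering in late 2016 cannot reach 5 years by December 2020. If the 30% and 45% already reflect usual care with later visits, the dilution is counted twice.

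**Existing safeguard.** The 12-month analysis does deal with a month-7 referral, and the list of sensitivity analyses is open-ended. It does not reach later years.

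**Conclusion.** The point holds as a gap between what Aim 2 estimates and how hypothesis 2 is worded, together with a missing rule for later cardiology visits and for the control's status at time zero. It rests on the text of sections 4, 12.1 and 12.2 and needs no outside figure.

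The size is unknown. The power figures are conditional on an assumed 3% to 8% yearly rate and full benefit, and smaller benefits give smaller losses. They show that the stated power for blood pressure and lipids depends on almost no effective cardiology care among controls. They do not show that the study is underpowered by a given amount or that the estimate is biased in a given direction.

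The 8-year horizon applies to events only, and with accrual over 2012–2016 only the earliest entrants approach it.

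This is an inexpensive change worth making because it affects what a null or fading difference can be taken to mean.

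**What to change.** In section 12.2:

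1. Label the planned comparison as the effect of early kept referral, and require that the control has had no cardiology visit between baseline and the pair's time zero.
2. Pre-specify one further analysis aligned with hypothesis 2. Either censor controls at their first later cardiology visit, with inverse-probability-of-censoring weights, or treat cardiology visit as a time-varying exposure. Unweighted censoring would be informative if visits follow worsening risk. Build the weights from the time-updated data listed in section 8.1, such as systolic pressure, lipids, antihypertensive prescriptions, diabetes, smoking, CD4 count and viral load. The Charlson index is planned at baseline only, so the weights should not depend on updating it.
3. Report the cumulative proportion of controls seen by cardiology, by year, beside the yearly blood pressure and lipid control rates. State in 12.2.1 that the power figures assume no such visits.

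Matching each referred patient to someone not yet seen at time zero, whatever happens afterwards, would remove the dependence on later information. It also admits more early crossover, so it suits a sensitivity analysis and should not replace the planned control definition.

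**Cost.** Protocol wording and extra programming. Section 12.1 already derives time to first cardiology visit, so no new data are needed. The censored analysis has less follow-up and relies on a weighting model.

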#### 7.3.2 Patient EHR data for Exclusion criteria for Aims 1 and 2:

- (1) Age <18 years of age or >99 years of age at index event;
- (2) Pre-existing ASCVD prior to index event, including a previous diagnosis of any acute myocardial infarction, heart failure, acute coronary syndromes, stable or unstable angina, arterial

revascularization (includes coronary arterial or peripheral), stroke, transient ischemic attack or peripheral arterial disease presumed to be of atherosclerotic origin determined by ICD codes;

- (3) Encounter with cardiology specialist within 1 year prior to index
- (4) Evidence of ART for pre-exposure prophylaxis (i.e., Truvada [emtricitabine/tenofovir disoproxil fumarate] or post-exposure prophylaxis (e.g., Truvada plus raltegravir) without HIV diagnosis.

## 7.4 Inclusion and exclusion criteria for Aim 3

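### Coronary artery disease by diagnosis code is counted as an outcome from the cardiology visit itself, so detection at that visit biases the CAD hazard ratio against referral

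*Combined protocol and SAP*

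**What the plan says.** Section 12.2 (Analysis Plan for Aim 2) includes among the secondary outcomes "coronary artery disease (based on diagnosis codes or coronary artery revascularization procedure"). Either route qualifies.

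The same section sets time zero for both members of a pair at the point "when the referred patient kept their cardiology appointment", and adds: "Events will be ascertained starting from time zero and until the end of follow-up". It then fits a Cox model to each outcome variable and reports the hazard ratio, 95% CI and p-value at the two-sided 0.05 level. CAD therefore gets its own test of referred against non-referred.

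Three other parts of the plan bear on this:

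- **Prior disease.** Section 7.3.2 excludes "Pre-existing ASCVD prior to index event, including a previous diagnosis of any acute myocardial infarction, heart failure, acute coronary syndromes, stable or unstable angina", followed by revascularization, stroke, TIA and peripheral arterial disease. The check is made before index, not before time zero, and chronic CAD by code is not named.
- **Testing.** Hypothesis 2a in Section 4 names cardiac testing among the care expected to mediate the effect of referral.
- **Composite.** Section 12.2 prints "MACE = cardiovascular death, myocardial infarction (MI)), stroke, heart failure hospitalization" and goes on to PAD procedure, CAD and all-cause death. The MACE bracket closes after MI. Section 4 says that "secondary outcomes are myocardial infarction, stroke, death and cardiovascular death both individually and as a composite".

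**The concern.** The exposure is a cardiology visit, and the visit is also an occasion on which CAD is looked for and coded. A patient with unrecognised or uncoded CAD who keeps the appointment can receive a first CAD code that day, or after the testing that follows. Under the plan that code is an incident event in the referred group. A matched patient with the same disease has no such visit at time zero and stays event-free until something else brings the disease to light.

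Section 5 states the central hypothesis that referral reduces incident CVD events. A CAD hazard ratio above 1 could be read as harm, or as lack of benefit, when it reflects diagnosis.

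**Working it through.** **1. What the plan does to prevent this.** Index and time zero differ. Section 12.1 allows 6 months from index to referral and 3 months from referral to the kept visit, so time zero can fall up to about 6 + 3 = 9 months after the prior-disease check. The sensitivity analyses in Section 12.1, which Section 12.2 carries over, are restriction to patients in routine follow-up, a 12-month referral window, and exclusion of subgroups with extreme referral rates. None deals with codes entered at or soon after the visit. No lag, confirmation rule or procedure-only version of CAD is given.

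**2. The plan's own event figures.** Section 12.2.1 expects MACE of about 5% at 5 years and about 10% at 10 years. A constant hazard of −ln(0.95)/5 = 0.01026 per year gives 1 − exp(−0.1026) = 9.75% at 10 years, so the two figures agree. With 300 per group, uniform accrual over 2012–2016 and follow-up to the end of 2020 capped at 8 years (mean 6.4 years), about 38 events are expected with no effect. Power is about 46% for a true hazard ratio of 0.5 and about 17% for 0.7, consistent with the plan's description of its power as modest. These are MACE figures. The plan gives no CAD rate.

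**3. Inputs for CAD alone.**
- n = 300 per group (Section 12.2.1).
- Background CAD by code at 5 years, b: assumed 3%, with 5% as an alternative.
- Excess of referred patients given a CAD code because of the visit, x: assumed 2%, 5% or 10%.
- No true effect of referral.

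**4. Formulas.**
- Non-referred incidence p0 = b; referred incidence p1 = 1 − (1 − b)(1 − x).
- Apparent hazard ratio = ln(1 − p1)/ln(1 − p0) = 1 + ln(1 − x)/ln(1 − b).
- Events = 300 × (p0 + p1).
- Chance of a significant result against referral ≈ Φ(ln HR × √(events/4) − 1.96).

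**5. Results.**

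| b | x | p1 | Events | Apparent HR | Chance of significant harm |
|---|---|---|---|---|---|
| 3% | 2% | 4.94% | 23.8 | 1.66 | 24% |
| 3% | 5% | 7.85% | 32.6 | 2.68 | 80% |
| 3% | 10% | 12.70% | 47.1 | 4.46 | >99% |
| 5% | 2% | 6.90% | 35.7 | 1.39 | 17% |
| 5% | 5% | 9.75% | 44.3 | 2.00 | 64% |
| 5% | 10% | 14.50% | 58.5 | 3.05 | 99% |

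One row in full (b = 3%, x = 5%): p1 = 1 − 0.97 × 0.95 = 0.0785; HR = 1 + 0.05129/0.03046 = 2.68; events = 300 × 0.1085 = 32.55; Φ(0.987 × √8.14 − 1.96) = Φ(0.86) = 0.80.

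**6. Masking a benefit.** With true hazard ratio θ, the excess that brings the apparent ratio to 1 is x = 1 − (1 − b)^(1 − θ). For θ = 0.5 this is 1.5% at b = 3% (about 5 of 300 patients) and 2.5% at b = 5% (about 8 of 300).

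**7. Cross-check by simulation.** Cox models were fitted to simulated data with a 5% background at 5 years, the accrual and follow-up in step 2, and excess codes placed in the first 90 days. With no true effect the median hazard ratios were 1.30, 1.81 and 2.65 for excesses of 2%, 5% and 10%, with significant harm in 15%, 56% and 96% of runs. These ratios are a little below the 5% rows above because follow-up averages 6.4 years, so background events dilute an early excess. With the excess codes removed and counting started at 90 days, the median returned to 0.98.

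**The case against.** **Scope.** A reader might infer that the whole event comparison is biased. The documents do not support that. Each outcome has its own model, and a CAD code does not enter the models for CV death, MI, stroke or all-cause death. The co-primary blood pressure and lipid outcomes are likewise untouched. CAD is in neither printed composite: Section 12.2 closes the MACE bracket after MI, and Section 4 lists MI, stroke, death and CV death. This limit stands.

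**Composite figures.** If the bracket is misplaced and CAD belongs in MACE, adding 3% CAD to a 5% event rate gives composite hazard ratios of 1.25, 1.63 and 2.29 for the same excesses. These should not be quoted as describing the plan's MACE. They need a reading that is not printed, and if MACE did include CAD, the plan's 5% would already contain it.

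**Contrast between groups.** Non-referred means not referred within 6 months and seen within 3 months of referral. Such patients may see a cardiologist later and may be coded by other clinicians at any time. The difference is one of timing and intensity, so the excess may shrink over follow-up. This affects size, not direction at the start of follow-up.

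**Two separate matters.** The differing composites do not cause detection bias, and Section 4 does not use the term MACE. They need reconciling in their own right, and the answer decides whether the bias reaches the composite.

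**Weight.** The plan already presents events as secondary and mainly informative about rates. That limits the consequence, but CAD still gets a hazard ratio and a p-value.

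**Conclusion.** The point holds for one secondary outcome. As written, the plan yields a CAD hazard ratio biased against referral, because a code alone counts, counting begins at the cardiology visit, and nothing in the exclusions or sensitivity analyses addresses codes arising from that visit.

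The direction follows from the text; the size does not. The ratios of about 1.7, 2.7 and 4.5 (about 1.4, 2.0 and 3.1 with a 5% background) rest on an assumed CAD rate, an assumed detection excess, proportional hazards over 5 years and no true effect. What is robust is that events are few: at these background rates, five to eight extra codes among 300 referred patients would hide a halving of CAD risk.

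A finding of bias in MACE, or in CVD events generally, is not supported unless CAD is placed inside the composite. The plan should be changed on this point, but its primary analysis is not in question.

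**What to change.** 1. Require both members of a pair to have no CAD code before time zero. Start counting code-based CAD after a fixed lag, for example 90 days, applied identically to both members. Treat CAD first coded inside that window, including on the visit day, as prevalent.
2. Add a version of the outcome limited to revascularization procedures, and label the code-based CAD hazard ratio as subject to detection. Dropping CAD from the comparative models altogether is possible but not necessary.
3. Separately, reconcile Section 4 and Section 12.2 into one MACE definition, say where the bracket closes, and keep code-only CAD out of it.

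The cost is protocol and SAP wording plus extra programming on data already extracted. There will be slightly fewer CAD events in an outcome with little power. A lag does not remove later differences in detection: disease still uncoded in matched patients may surface after the window and tilt the comparison the other way. Revascularization can also follow from testing, though less directly than a code. That is why the procedure-only version and the label are needed as well as the lag.
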